6.6. Sample Size Analysis

The sample size chosen in the post-market trial is 50 patients. The adequacy of this sample size was verified, see table below. The width of the confidence interval provide information about precision of the estimates about the unknown parameter. Confidence intervals are more informative than the simple results of hypothesis tests (namely, conclusion to "reject H0" or "don't reject H0") since they provide a range of plausible values for the unknown parameter.

Reference safety rates are based on published literature, and assume a 2-tailed alpha of 5% in order to build 95% confidence intervals for the outcome of interest. According to the computations, a sample size of 50 patients provides adequate precision for statistical inference concerning endpoints, even those with low incidence.

7. DATA COLLECTION AND MANAGEMENT

7.1. Data Management Activities

Data Management activities include, but are not limited to, collecting and tracking data and instituting quality control measures for data entry verification and trial compliance. The Sponsor and the Data Management Center will review significant new information, including adverse events and deviations from the clinical protocol, and ensure that such information is provided to relevant parties including Regulatory Authorities, Investigators, ECs as required by local and national regulations and this Clinical Investigational Plan.

Study data will be reviewed during regular Investigator meetings.

The Data Management Center for the study is:

Sunshine Heart Inc.
[name]
[name]
USA

7.2. Information Collected in the Electronic Case Report Forms (e-CRFs)

The study physician or his designee at each clinical site will perform primary data collection. Only the study physician or other pre-designated study personnel will be authorized to enter data (from source documents) via internet-based e-CRFs. Study personnel will each be assigned a unique user name and pass code to access the e-CRFs. Representatives, agents or consultants of the Data Management Center, the Sponsor or other designee will provide training, clinical monitoring, including review of e-CRFs with verification to the source documentation.

Study patients will be enrolled based on the current approved labeling (as outlined in the Instructions for Use). Eligibility for each patient enrolled will be based on the current CE mark labeling and will be documented appropriately in the medical records (source documents) and entered in the e-CRFs.

Only anonymous data will be collected after the patient has consented that personal data can be used. Patients treated with the study device are asked to consent in writing that their data can be entered into a central database.

7.3. Patients Lost to Follow-up

Patients that refuse to make their data available at a certain time point will be considered "lost to follow-up". The data that has been obtained from a patient that was subsequently lost to follow-up may still be used in any subsequent analysis.

7.4. Source Documents

The study physician or his designee at each clinical site will perform primary data collection. Only the study physician or other pre-designated study personnel will be authorized to enter data (from source documents) via internet-based e-CRFs. Study personnel will each be assigned a unique user name and pass code to access the e-CRFs. Representatives, agents or consultants of Data Management Center, the Sponsor or other designee will provide training, clinical monitoring, including review of e-CRFs with verification to the source documentation.

Source documentation may include any of the following:

1. Medical history/physical condition of the study subject before involvement in the study.

2. Dated and signed notes in the subject's medical record on the day of entry into the study that identify:
 - a. the subject's date of entry into the study, the study Sponsor, the clinical site, the subject number
 - b. A signed statement that informed consent was obtained.
 - c. Dated and signed notes from each study subject visit with reference to the e-CRFs for further information, if appropriate (for specific results of procedures and exams).
 - d. Description of device implantation procedure (material used, drugs administered during the procedure, date, time duration, echocardiographic and clinical findings, etc.).
3. Notations on abnormal lab results and their resolution.
4. Dated printouts or reports of special assessments, i.e., ECG reports.
5. Adverse event reporting and follow-up of the adverse events (event description, severity, onset date, duration, relation to study device, outcome and treatment for adverse event).
6. Notes regarding concomitant medications taken during the study (including start and stop dates).
7. Study subject's condition upon completion of or withdrawal from the study.

Periodic teleconference calls between Sponsor or CRO and each clinical site may be performed to resolve any issues concerning the e-CRF and data collection methods.

7.5. Site Documentation

Each clinical site will maintain a Regulatory Binder in which the following documents will be maintained:

1. Signed Investigator and Institutional Agreement
2. Signed Study Protocol and Amendments including:
 - a. Device Instructions for Use
 - b. Electronic Case Report Forms and completion guidelines
3. All Investigator and Co-Investigator CVs and Medical Licenses
4. If applicable for the participating site:
 - a. EC documents, including member list and number
 - b. EC approval letter and updates
5. Master copy of EC approved informed consent, advertising and recruitment materials
6. General Correspondence
7. Delegation of Responsibilities/Duties
8. Patient Enrollment Logs
9. Site Visit Log & Reports

10. Study communications including:
 - a. Documentation of written and verbal communications with Sponsor
 - b. Documentation of written and verbal communications with other Investigators

7.6. Quality Assurance and Access

The Sponsor or designee will create and maintain the database as per its internal procedures and policies and in accordance with applicable regulations on personal data protection. The Sponsor or designee will also be responsible for verification and validation of the database (including applicable security methods).

Data entered into the e-CRF database are the sole property of the Sponsor and the frequency for review and use of the data will be at its discretion. Only designated Sponsor personnel are authorized to access the database.

7.7. Monitoring Plan

The Sponsor or designee will perform site monitoring during the Clinical Trial to ensure compliance with the Clinical Investigation Plan and applicable regulations, that data is collected in a timely, accurate and complete manner and that the Investigator continues to have appropriate staff and facilities to conduct the Clinical Trial safely and effectively. Monitoring will be performed in accordance with a pre-specified monitoring plan that is in compliance with applicable Standard Operating Procedures.

7.8. Data Retention

All study records and reports must remain on file for a minimum of ten (10) years after the completion or termination of the study. Study records are to be discarded only upon notification by the Sponsor.

The study physicians should contact the Sponsor before the destruction of any records and reports pertaining to the study to ensure they no longer need to be retained. In addition, the Sponsor should be notified if the study physician plans to leave the institution.

7.9. Study Closeout

Upon completion of the study (when all subjects enrolled have been followed at 5 years and the e-CRFs and queries have been completed), a close-out visit will be performed. All unused study materials and equipment will be collected and returned to the Sponsor or designee. Items that will be reviewed at this visit include: discussing retention of study files, publication policy, and to ensure that the study physician will notify the local ethics committee and/or competent authority regarding study closure, if needed.

7.10. Final Report

The Sponsor will generate a final report at the close of the study. The final report will include a descriptive analysis of the clinical data for all study cohorts.

8. PROCEDURE FOR ADVERSE EVENT MANAGEMENT

8.1. Reporting Procedure

Adverse event information will be reported throughout the clinical investigation as they occur. Adverse events will be followed until they are adequately resolved or explained. A *list of potential AEs, which may result from the study procedure, is included as part of the IFU.*

The investigator(s) will report any serious adverse event to the Sponsor's Clinical Research department no later than three calendar days after the Investigator first learns of the event, followed by a written report within ten working days. This reporting will be done via data entry in the electronic CRF: the sponsor will receive an email alert for each serious adverse event that is entered.

In addition, investigational centers will report all serious adverse events to their local EC and National Competent Authority in accordance with the review committee's and national requirements.

The Sponsor or its designee will determine requirements of reporting adverse events according to its responsibilities for medical device vigilance.

8.2. Definitions

For purposes of this protocol adverse event definitions are taken from the guidance ISO document; please refer to EN ISO 14155:2011.

8.2.1. . Adverse Event

An adverse event (AE) is defined as any untoward medical occurrence, unintended disease or injury, or untoward clinical signs (including abnormal laboratory findings) in subjects, users or other persons, whether or not related to the investigational medical device.

NOTE 1: This definition includes events related to the investigational medical device or the comparator.

NOTE 2: This definition includes events related to the procedures involved.

NOTE 3: For users or other persons, this definition is restricted to events related to investigational medical devices.

8.2.2. . Adverse Device Effect

An adverse device effect (ADE) is defined as any adverse event related to the use of an investigational medical device.

NOTE 1: This definition includes adverse events resulting from insufficient or inadequate Instructions for Use, deployment, implantation, installation, or operation, or any malfunction of the investigational medical device.

NOTE 2: This definition includes any event resulting from use error or from intentional misuse of the investigational medical device.

8.2.3. . Serious Adverse Event

A serious adverse event (SAE) is defined an adverse event that:

- a. led to death,

b. led to a serious deterioration in the health of the subject, that either resulted in:

1. a life threatening illness or injury, or
2. a permanent impairment of a body structure or a body function, or
3. in patient or prolonged hospitalization, or
4. medical or surgical intervention to prevent life threatening illness or injury or permanent impairment to body structure or a body function,

c. led to fetal distress, fetal death or a congenital abnormality or birth defect.

NOTE: Planned hospitalization for a preexisting condition, or a procedure required by the CIP, without serious deterioration in health, is not considered a serious adverse event.

The serious adverse events will be reported into the following categories:

8.2.4. . Adverse Event Definitions

Definitions are listed below for anticipated adverse events. The definitions are consistent with Version 2.2 adverse event definitions for the INTERMACS™ registry with the exception of Major Bleeding which does not have a minimum standard of transfusion. Aortic Disruption has been added in addition to the INTERMACS™ registry definitions as an additional screening for safety with respect to the C-Pulse unique application. Worsening Heart Failure has been added due to C-Pulse System not being a heart function replacement rather a heart assist device and based on the definition used by the CEC in the US Feasibility study.

Major Bleeding

An episode of suspected internal or external bleeding that results in one or more of the following:

1. death
2. re-operation
3. hospitalization
4. transfusion of red blood cells

NOTE: Hemorrhagic stroke is considered a neurological event and not as a separate bleeding event.

Cardiac Arrhythmias

Any documented arrhythmia that results in clinical compromise (e.g. oliguria, pre-syncope or syncope) that requires hospitalization or occurs during a hospital stay. Cardiac arrhythmias are classified as 1 of 2 types:

- 1) Sustained ventricular arrhythmia requiring defibrillation or cardioversion.
- 2) Sustained supraventricular arrhythmia requiring drug treatment or cardioversion.

Pericardial Fluid Collection

Accumulation of fluid or clot in the pericardial space that requires surgical intervention or percutaneous catheter drainage. This event will be subdivided into those with clinical

signs of tamponade (e.g. increased central venous pressure and decreased cardiac output) and those without signs of tamponade.

Aortic Disruption

Disruption to the intima of the ascending aorta. Disruption may be partial or complete (i.e. transmural), and the latter may result in contained or free rupture. Typically this would be documented initially by CT scan with or without contrast or by trans-esophageal echocardiography.

Device Malfunction

Device malfunction denotes a failure of one or more of the components of the MCSD system which either directly causes or could potentially induce a state of inadequate circulatory support (low cardiac output state) or death. The manufacturer must confirm device failure. A failure that was iatrogenic or recipient-induced will be classified as an Iatrogenic/Recipient-Induced Failure.

Device failure should be classified according to which components fails as follows:

- 1) **Pump** failure (implanted components of pump and any motor or other pump actuating mechanism that is housed with the implanted components). In the special situation of **pump thrombosis**, thrombus is documented to be present within the device or its conduits that result in or could potentially induce circulatory failure.

Note: For C-Pulse system – this includes the Cuff and Gas line and/or ECG lead.

- 2) **Non-pump** failure (e.g., external pneumatic drive unit, electric power supply unit, batteries, controller, interconnect cable, compliance chamber).

Note: For C-Pulse system – this includes the Percutaneous Interface Lead and the Driver.

Hemolysis

A plasma-free hemoglobin value that is greater than 40 mg/dl, in association with clinical signs associated with hemolysis (e.g., anemia, low hematocrit, hyperbilirubinemia) occurring after the first 72 hours post-implant. Hemolysis related to documented non-device-related causes (e.g. transfusion or drug) is excluded from this definition.

Hepatic Dysfunction

An increase in any two of the following hepatic laboratory values (total bilirubin, aspartate aminotransferase/AST and alanine aminotransferase/ALT) to a level greater than three times the upper limit of normal for the hospital, beyond 14 days post-implant (or if hepatic dysfunction is the primary cause of death).

Hypertension

New onset blood pressure elevation greater than or equal to 140 mm Hg systolic or 90mmHg diastolic (pulsatile pump) or 110mmHg mean pressure (rotary pump).

Major Infection

A clinical infection accompanied by pain, fever, drainage and/or leukocytosis that is treated by anti-microbial agents (non-prophylactic). A positive culture from the infected site or organ should be present unless strong clinical evidence indicates the

need for treatment despite negative cultures. The general categories of infection are listed below:

Localized Non-Device Infection

Infection localized to any organ system or region without evidence of systemic involvement (see sepsis definition), ascertained by standard clinical methods and either associated with evidence of bacterial, viral, fungal or protozoal infection, and/or requiring empirical treatment.

Percutaneous Site and/or Pocket Infection (PIL Only)

A positive culture from the skin and/or tissue surrounding the drive line or from the tissue surrounding the external housing of a pump implanted within the body, coupled with the need to treat with antimicrobial therapy, when there is clinical evidence of infection such as pain, fever, drainage or leukocytosis.

Internal Pump Component, Inflow or Outflow Tract Infection (Cuff, ECG Lead and Gas line not including the PIL)

Infection of the implanted C-Pulse Cuff or surrounding tissue (e.g. aorta) documented by positive site culture.

Sepsis

Evidence of systemic involvement by infection, manifested by positive blood cultures and/or hypotension.

Myocardial Infarction

Two categories of myocardial infarction will be identified:

Peri-Operative Myocardial Infarction

The clinical suspicion of myocardial infarction together with CK-MB or Troponin > 10 times the local hospital upper limits of normal, found within 7 days following implant together with ECG findings consistent with acute myocardial infarction.

Non-Perioperative Myocardial Infarction

The presence at > 7 days post-implant of two of the following three criteria:

- a) chest pain which is characteristic of myocardial ischemia,
- b) ECG with a pattern or changes consistent with a myocardial infarction, and
- c) Troponin or CK (measured by standard clinical pathology/laboratory medicine methods) greater than the normal range for the local hospital with positive MB fraction ($\geq 3\%$ total CK). This should be accompanied by a new regional LV or RV wall motion abnormality on a myocardial imaging study.

Neurological Dysfunction

Any new, temporary or permanent, focal or global neurological deficit ascertained by a standard neurological examination (administered by a neurologist or other qualified physician and documented with appropriate diagnostic tests and consultation note). The examining physician will distinguish between a transient ischemic attack (TIA), which is fully reversible within 24 hours (and without evidence of infarction), and a stroke, which lasts longer than 24 hours (or less than 24 hours if there is evidence of infarction). The NIH Stroke Scale (for patients > 5 years old) must be re-administered at 30 and 60 days following the event to document the presence and severity of neurological deficits. Each neurological event must be subcategorized as:

- 1) Transient Ischemic Attack (acute event that resolves completely within 24 hours with no evidence of infarction)

2) Ischemic or Hemorrhagic Cerebrovascular Accident/CVA (event that persists beyond 24 hours or less than 24 hours associated with infarction on an imaging study).

Psychiatric Episode

Disturbance in thinking, emotion or behavior that causes substantial impairment in functioning or marked subjective distress requiring intervention. Intervention is the addition of new psychiatric medication, hospitalization, or referral to a mental health professional for treatment. Suicide is included in this definition.

Renal Dysfunction

Two categories of renal dysfunction will be identified:

Acute Renal Dysfunction

Abnormal kidney function requiring dialysis (including hemofiltration) in patients who did not require this procedure prior to implant, or a rise in serum creatinine of greater than 3 times baseline or greater than 5 mg/dL (**in children**, creatinine greater than 3 times upper limit of normal for age) sustained for over 48 hours.

Chronic Renal Dysfunction

An increase in serum creatinine of 2 mg/dl or greater above baseline, or requirement for hemodialysis sustained for at least 90 days.

Respiratory Failure

Impairment of respiratory function requiring reintubation, tracheostomy or (for patients older than age 5 years) the inability to discontinue ventilatory support within six days (144 hours) post-implant. This excludes intubation for re-operation or temporary intubation for diagnostic or therapeutic procedures.

Right Heart Failure

Symptoms and signs of persistent right ventricular dysfunction [central venous pressure (CVP) > 18 mmHg with a cardiac index <2.0 L/min/m² in the absence of elevated left atrial/pulmonary capillary wedge pressure (greater than 18 mmHg), tamponade, ventricular arrhythmias or pneumothorax] requiring RVAD implantation; or requiring inhaled nitric oxide or inotropic therapy for a duration of more than 1 week at any time after implantation.

Worsening Heart Failure

A heart failure event requiring hospitalization including the following:

- Signs and symptoms of worsening heart failure; and
- Treatment with intravenous heart failure therapy (including but not limited to diuretic or inotropic therapy); and
- A minimum of one date change in the hospital or emergency room

Arterial Non-CNS Thromboembolism

An acute systemic arterial perfusion deficit in any non-cerebrovascular organ system due to thromboembolism confirmed by one or more of the following:

- 1) standard clinical and laboratory testing
- 2) operative findings
- 3) autopsy findings

This definition excludes neurological events.

Venous Thromboembolism Event

Evidence of venous thromboembolic event (e.g. deep vein thrombosis, pulmonary embolism) by standard clinical and laboratory testing.

Wound Dehiscence

Disruption of the apposed surfaces of a surgical incision, excluding infectious etiology, and requiring surgical repair.

Other

An event that causes clinically relevant changes in the patient's health (e.g. cancer).

8.2.5. . Serious Adverse Device Effect (SADE)

A serious adverse device effect (SADE) is defined as an adverse device effect that results in any of the consequences characteristics of a serious adverse event.

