The C-Pulse® System is also indicated for use in patients who are non-responders to CRT pacemaker therapy. It is intended for use in hospital and at home. It is not intended as a replacement for heart function; it is not life sustaining or life-supporting therapy. It does not preclude the use of other heart failure therapies, such as valve surgery, heart transplantation or LVAD.

2.3. . Mechanism of Action

2.3.1. 1. C-Pulse Cuff Design and Operation

The C-Pulse® Cuff is designed to displace blood from the ascending aorta during diastole when inflated and to restore normal anatomic structure deflating before systole. The volume displacement of the extra-aortic cuff, by virtue of the short ascending aorta, is limited compared to the descending Intra-aortic Balloon (IAB) capacity, but the proximity of the C-Pulse to the aortic valve is expected to allow equivalent or better counterpulsation compared to methods of descending aortic counterpulsation.

The balloon is intended to inflate and deflate in a manner that causes the least possible strain to both the balloon material and to the aorta while maximizing blood volume displacement within the ascending aorta. The balloon is inflated to a volume typically 15-20% less than its

natural volume. Inflating the balloon further does not achieve significantly greater volume displacement but does lead to a higher intra-balloon pressure. Thus, the optimal balloon inflation point results in a small (approximately 5-10 mmHg) transmural pressure between the inflated cuff and the aorta whilst displacing close to optimal volume per beat.

The balloon is designed to not occlude the aorta when fully inflated. A dipping process is utilized to manufacture the balloon from DSM Biomedical's (DSM) proprietary BioSpan® segmented polyurethane (an FDA master file material). The balloon is manufactured in its inflated shape and is stored and supplied in this stress free state. This material exhibits high strength, flexibility, and fatigue resistance together with biological compatibility and biostability. Furthermore, the material has a long history of use in permanent cardiovascular implants.

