4.3 C-PULSE SYSTEM Risks

Implantation is an invasive procedure requiring a sternotomy or thoracotomy and the use of general anesthesia and mechanical respiratory support. The potential risks associated with the implant procedure also include those associated with any cardiothoracic surgery, including implantation of devices and include the following:

- Bleeding
- Infection
- Neurological Dysfunction
- Renal Dysfunction
- Cardiac Arrhythmias
- Pericardial Fluid Collection
- Aortic Disruption
- Device Malfunction

- Hemolysis
- Hepatic Dysfunction
- Hypertension
- Myocardial Infarction
- Psychiatric Episode
- Respiratory Failure
- Right Heart Failure
- Arterial Non-CNS Thromboembolism
- Wound Dehiscence
- Death

Potential Adverse Effects may include Damage to the C-Pulse Cuff on implantation or misplacement of the ECG lead – not able to sense 'R' wave appropriately. There have been no unanticipated adverse events during the premarket clinical study. Percutaneous Interface Lead (PIL) failures and infections were the two areas of risk identified by Risk Analysis and confirmed during the C-Pulse clinical study.

PIL Failures

The risk associated with the PIL failures are related to the PIL replacement procedure. The only risks would involve re-hospitalization and minor superficial surgery. There have been no observed complications with PIL removal and replacement during the C-Pulse® study. Therefore, based upon current clinical experience, the risk is low.

Sunshine Heart has addressed the cause of the device failures. The risk of PIL failure occurrence has been mitigated by design changes which address 1) the wire breakages related to cyclic fatigue, 2) kinking and 3) IS1 insertion. Implementation of these design changes will mitigate the risk of occurrence of the PIL failures to an acceptable low level. The changes will reduce the observed PIL failures to 5% (1/20).

The clinical benefit of the PIL and its design features, e.g. ease of accessibility, ability for the patient to temporarily disconnect, and modular design for ease of replacement outweigh the residual risk. The PIL is essential in order to reduce exit site infection clinical consequences.

Infections

The infections and associated risk levels observed during the clinical study may be subdivided into different levels based upon risk to the patient and clinical management:

1) Exit site related infection

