6.4. Safety Endpoints

The following primary safety endpoints will be assessed throughout each subject's participation in the investigation:

- All cause and device-related mortality
- Aortic disruption
- Exit Site infection
- Internal PIL/Cuff infection
- Thromboembolism
- Device malfunction
- All protocol-defined adverse events

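### The severity threshold in the Device Malfunction definition fits this device poorly, so Percutaneous Interface Lead (PIL) failures may be under-counted or counted inconsistently in a primary safety endpoint

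*Combined protocol and SAP*

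**What the plan says.** Section 6.4 opens its list with "The following primary safety endpoints will be assessed throughout each subject's participation in the investigation", and "Device malfunction" is on that list.

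Section 8.2.4 defines it as a failure of one or more system components that directly causes or "could potentially induce a state of inadequate circulatory support (low cardiac output state) or death". It adds: "The manufacturer must confirm device failure". Failures are then sorted into pump and non-pump. A C-Pulse note assigns the Cuff, gas line and ECG lead to the first class, and the PIL and Driver to the second.

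The introduction to 8.2.4 says the definitions follow version 2.2 of the INTERMACS registry. It names the departures: Major Bleeding is changed, and Aortic Disruption and Worsening Heart Failure are added. Device Malfunction is not among them.

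Other sections describe what happens when this device stops:

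- Section 2.2: "it is not life sustaining or life-supporting therapy".
- Section 2.3.5: the natural path of blood flow is preserved if the balloon no longer inflates.
- Section 4.3, on PIL failures: "The only risks would involve re-hospitalization and minor superficial surgery".

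Section 4.3 also names PIL failure and infection as the two risk areas confirmed in the premarket study, and projects that design changes will bring PIL failures down to 5% (1/20).

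**The concern.** The threshold was written for pumps on which the circulation depends. The protocol presents C-Pulse as an assist device that can be disconnected. Take a patient whose PIL wire breaks, who loses therapy, is re-admitted and has the PIL replaced. A site that reads 8.2.4 literally, with Section 4.3 in hand, can conclude that low output or death was never in prospect and record no malfunction. A second site can judge that losing counterpulsation in a patient with refractory NYHA Class III/IV heart failure could leave support inadequate, and record one. The text does not settle which is right.

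The note naming the PIL and Driver shows that PIL failures are meant to belong here. But it says how to classify a device failure and does not lift the threshold in the opening sentence.

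This matters because Section 4.1 gives the study's purpose as monitoring safety and performance and confirming the premarket results, and the analysis is descriptive (Sections 6.5 and 7.10). The count is itself the result. A low malfunction rate could reflect a reliable PIL, or PIL failures judged not to qualify, and the endpoint alone would not show which.

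**Working it through.** **Inputs.** N = 50 (Section 6.6; elsewhere stated as up to 50). Projected PIL failure proportion p = 5% (Section 4.3). Two-sided 95% intervals (Section 6.6). Assumptions not in the documents: true rates of 10% and 20%, and a share s of PIL failures judged to pass the threshold (s = 1, 0.5 or 0). Patients are treated as independent, and 5% as a per-patient proportion over the study; the protocol gives no time horizon for it.

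**The plan's own figure.** 1/20 = 5.0%, so the arithmetic holds. It is a projection, and its derivation is not shown.

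**Full counting at 5%.**

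- Expected patients with a PIL failure: 50 × 0.05 = 2.5.
- Chance of none: 0.95^50 = 0.077, or 7.7%. Chance of at least one: 92.3%.

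**If no PIL failure qualifies.** The PIL count is 0/50 by construction. The exact (Clopper-Pearson) upper limit is 1 − 0.025^(1/50) = 0.071, so the interval is 0 to 7.1%. It includes 5%, so complete under-counting would look compatible with the projection.

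**Chance of a zero PIL count,** (1 − p·s)^50:

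| True rate p | Expected, all counted | s = 1 | s = 0.5 | s = 0 |
|---|---|---|---|---|
| 5% (projected) | 2.5 | 7.7% | 28.2% | 100% |
| 10% (assumed) | 5 | 0.5% | 7.7% | 100% |
| 20% (assumed) | 10 | 0.001% | 0.5% | 100% |

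At the projected rate, if half the failures pass, the chance of a zero count rises from 7.7% to 28.2%. In the last column the count carries no information about the true rate.

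**What full counting can deliver.** 2/50 is 4.0% (95% CI 0.5 to 13.7%) and 3/50 is 6.0% (1.3 to 16.5%). Even a clean count gives a wide interval.

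**The case against.** A reader might infer that the protocol says failures of this device cannot cause inadequate support, so that PIL failures must score zero. The documents do not support that.

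- No section says it. The Clinical Risk/Benefit Assessment says only that the risk from device failure is much lower than with devices in the bloodstream. Not being life-sustaining does not mean that losing therapy leaves output adequate, and a preserved flow path is not the same as adequate flow.
- The Section 4.3 sentence follows one that ties the risk of PIL failure to the replacement procedure. It is most naturally about that surgery, and it covers the PIL only, not the Cuff or Driver. The same section reports an infection after a PIL breach, with risks called high if it is not properly managed.
- The phrase about potential to induce low output is broad. A reading under which no PIL failure could ever qualify would empty the PIL part of the classification note.

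All of this stands. It makes zero one possible reading and moves the defect from exclusion to ambiguity.

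There are also other capture routes. The adverse device effect definition (8.2.2) covers adverse events from any malfunction, with no low-output test. A hospitalization may qualify as a serious adverse event (8.2.3), and all protocol-defined adverse events are themselves a primary safety endpoint. Section 8.3.2 asks for reports and return of explanted components, and Table 3 schedules a device log. This also stands, in part. PIL replacements would usually leave a record, but not necessarily in the malfunction count: 8.2.3 sends serious events into the 8.2.4 categories, so one that misses the threshold could fall under Other, and the device log has no stated endpoint role.

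Finally, registry consistency is a deliberate choice, and Section 6.5 foresees possible pooling with the US trial. That argues for keeping the registry wording as a tier, not for leaving it as the only test.

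**Conclusion.** The concern holds as an ambiguity in a primary safety endpoint. The 8.2.4 threshold fits poorly with Sections 2.2, 2.3.5 and 4.3 and with its own component note, so PIL failures can be under-counted or counted differently by different readers.

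The size depends on how the threshold is read. At the projected 5%, the chance of a zero PIL count runs from 7.7% with full counting to 100% if none qualify; the latter is a bounding case, not a forecast. The 10% and 20% rates and the half share are illustrations.

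A reader might also infer that a better definition would let the study confirm the 5% projection. It would not: no hypothesis tests that figure, and the intervals at N = 50 are wide. The gain is a count that means the same thing at every site. SHOULD-FIX, moderate confidence.

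**What to change.** In Section 8.2.4, define Device Malfunction for C-Pulse as any confirmed failure of the Cuff, gas line, sense lead, PIL or Driver that interrupts or degrades therapy, or that leads to unplanned repair, replacement, revision or explant. Keep the registry wording as a severity sub-tier for failures that cause or could induce inadequate support or death. Report both tiers by component. The same edit can state whether failures classed as iatrogenic or recipient-induced stay in the count, which 8.2.4 leaves open.

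The cost is one wording change and one severity field in the e-CRF. The downside is that the headline malfunction rate will rise, and only the sub-tier stays comparable with the registry and, for any pooling, with the US trial.
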